**Sponsor:**

**Qatar National Priority Research Program**

**NPRP No.: NPRP 5 - 117 - 3 - 028**

## **1. Introduction and Purpose:**

Our long-term goal is to provide a convenient, low-cost therapeutic device and treatment protocol for diabetic patients with high risk of falling. Eventually, we plan for this to be an approach that can be used by patients at home. We will use preliminary data from this study to plan and implement a randomized clinical study in high risk diabetics to evaluate long-term clinical outcomes, specifically a reduction of falls, foot ulcers and amputations in patients that use the electrical stimulation treatment.

This study will be a double-blind randomized clinical trial design consisting of two groups of forty (40) patients with diabetic peripheral neuropathy and some level of postural instability. The study consists of a 12 weeks treatment phase and two weeks of retention. Subjects will be asked to wear a comfortable electrical stimulation device (SENSUS™ Pain Management System, Neurometrix, Inc., Waltham, MA) during night time on daily basis for duration of 8 hours. The proposed dosage regimen was used in our preliminary studies and no related adverse event was reported while a significant improvement in skin perfusion was observed. The objective of this proposed study is threefold:

**Aim1:** To compare postural control in subjects assigned to use the active Electrical Stimulation (intervention group) and subjects assigned to non-functional stimulator (sham group). Balance will be assessed for both groups at baseline and at monthly intervals. Study hypotheses are:

**H1:** Electrical Stimulation will improve postural coordination and helps to reduce body sway during standing in the treatment group compared to the sham group as well as compared to the baseline.

**H2:** Electrical Stimulation will improve gait, gait initiation, and gait inter-cycle variability compared to the sham group as well as compared to the baseline.

**Aim2:** To compare changes in skin perfusion in patients treated with Electrical Stimulation compared to sham therapy.

**H3:** Electrical Stimulation will improve dorsal and plantar perfusion compared to the control group and compared to baseline.

**Aim3:** To evaluate changes in quality of life in high risk diabetes who received Electrical Stimulation compared to sham therapy.

**H4:** Plantar stimulation will improve subject quality of life in the intervention group assessed using SF36.

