**H5:** Plantar stimulation will improve spontaneous daily physical activity. More specifically, the duration of walking and standing as well as activity organization (i.e. day-to-day activity fluctuation) will be improved.

**H6:** The risk and fear of falling during activity of daily life will be improved.

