#### **4. Study Procedures:**

There will be a total of five study visits required for each patient. There will be one scheduled visit for baseline evaluation and four additional visits at 2 weeks, 4 weeks, 6 weeks during treatment and 8 weeks (2 weeks post stopping the treatment). The baseline visit will involve completion of a standardized intake form, which will include pertinent demographics such as age, height, weight, education level, occupation, and comorbidities of the study patient (see Table IV). Several clinical assessments will be performed at baseline as well as at each study visit to evaluate severity of neuropathy and skin perfusion as described in the table IV.

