
Baseline & each 2- week follow-up (week 2, week 4, week 6, and week 8)
 
+ 2 day visit window for each protocol related visit starting at Week 2.
	
Peripheral Neuropathy: We will evaluate Vibration Perception Threshold (VPT) Testing to evaluate large fiber neuropathy
 
We will also use Semmes-Weinstein monofilaments, and the Modified Neuropathy Disability Score. (Armstrong and Lawrence 1998) We will assess light touch and pressure sensation at nine sites on each foot using 4, 10, 26, and 60 Semmes-Weinstein gram monofilaments. (Diamond, Mueller et al. 1989) The Modified Neuropathy Disability Score is a scored clinical examination that includes Achilles deep tendon reflex, pressure, vibration sensation and temperature sensation in both feet. (Abbott, Carrington et al. 2002; Caselli, Spallone et al. 2006).
 
Pain: Visual Analogue Scale
 
Gait test: 8 sensors will be attached to the legs and lower back using comfortable straps and will be asked to walk 20 meters on a flat surface, two times. A third 20 meter walk will be performed with an additional distractive cognitive task (counting -1). The 4th test will be fast walking. Walking performance (e.g., speed, cadence, and stability) and spatio-temporal parameters of gait (e.g., velocity, stride time, gait inter-cycle variability, double support, and gait initiation) will be measured.
 
Balance test: The BalanSens™ kinematic sensor will be attached to the legs and lower back and will be used to measure the variation of subject's center of mass measured by the Romberg protocol including double stance, semi-tandem, and full-tandem tests. Patients will be asked to stand straight, feet together, hands crossed for 30 seconds, 20 seconds, and 15 seconds respectively for double stance test, semi-tandem, and full tandem tests with eyes open and closed.

Baseline and 6 weeks follow-up
	
Activity Monitoring: Spontaneous daily physical activity will be monitored in home environment for 2 days using PAMSys™
 
Removal log: participants will be asked to note the time off, time on, and reason for removal if the PAMSys™ is removed during the 2 day collection period. Refer to Activity Monitoring Log for times of use and removal.
 
Quality of life questionnaire: SF12 will be administered.

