
Other assessment
	
Fall log: participant will receive a log and agree to call the study overseer in the event of a fall during the 4 weeks study period.
 
Other patient information: if it was available patients record including medical history, neurological exam results, and physical examination may be gathered from patient record after authorization of the subject (see form T504a). In addition, subject photograph or video during experiment may be taken after subject's authorization.

Baseline & each 2- week follow-up	
Vascular Assessment: We will assess perfusion of the macro-circulation with arterial Doppler studies and micro-circulation with Skin Perfusion Pressure measurements and transcutaneous oxygen measurements. Ankle Brachial Index (ABI), Toe Pressures and Waveforms (pulse volume recordings) will be measured on both extremities. If the ankle is too painful to perform a Doppler examination, we will get Doppler measurements once the patient is in the operating room and under anesthesia. ABI's have been reported to be reliable measurements for diagnosing peripheral vascular disease. ABI's have a 95% sensitivity in detecting angiographically positive disease in an ABI of less than 0.9. Non-compressible foot vessels will be defined as ABI's <math>>1.30</math>. Peripheral arterial occlusive disease will be defined as an ABI <math><0.90</math>. Monckeberg's medial calcific sclerosis or calcification of the media of the arteries can limit the effectiveness of using ABI's in persons with diabetes. Therefore, we will use the SensiLase system (Väسامد) to measure Skin Perfusion Pressure (SPP) in mmHg and records PVR waveforms with its laser Doppler sensor and computer-automated cuff. This technique has high sensitivity and high positive and negative predictive value to predict amputation.(Castronuovo, Adera et al. 1997; Yamada, Ohta et al. 2008) In addition we will measure transcutaneous oxygen measurements at 2 sites on the foot and two sites on the lower leg during the course of therapy.

-----------------------------------	--

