Hypothesis 5: We also anticipate that plantar electrical stimulation will improve spontaneous daily physical activity. More specifically, the duration of walking and standing as well as activity organization (i.e. day-to-day activity fluctuation) will be improved. Spontaneous daily physical activity will be assessed using PAMSys™ designed and validated by [name] (PI) and his team with collaboration of Biosensics LLC. Participants will wear PAMSys□□ embedded in a lightweight breathable tank top worn under clothing for 2 consecutive days at baseline and each study visit (Fig 14). This device uses a combination of miniaturized kinematic sensors housed in a single portable sensor attached to the chest. It can detect body posture (sitting, standing, and lying), as well as provide an accurate assessment of periods of locomotion (e.g., walking, postural transition). The validity of this approach has been established in 3 separate pilot studies, and by benchmarking the results with independent analysis by an optical motion system.(Najafi, Aminian et al. 2002; Najafi, Aminian et al. 2003; Najafi, Wrobel et al. 2008; Najafi, Crews et al. 2010) These studies demonstrate that the PAMSys™ has an overall sensitivity of 99% for detecting the time of various postural transitions (e.g., sit-to-stand or stand-to-sit) and more than 87% sensitivity and specificity for identifying the transition type. *This fine-grained analysis of human movement represents a tremendous leap in technology over what is presently available.* Thus, this measurement technique will provide unique data, not previously acquired, on actual participation in daily life.

**Hypothesis 6:** Finally, we assumed that risk and fear of falling in the intervention group will be reduced compared to baseline and compared to sham group. To evaluate the fear of falling, we will use Fall Efficacy Scale (FES) questionnaire (Bula, Martin et al. 2006; De Bruin, Najafi et al. 2007). The risk of falling will be assessed using test timed Up&Go (Shumway-Cook, Brauer et al. 2000) as well as the duration required for rising or sitting on a chair as described by Najafi et al.(Najafi, Aminian et al. 2002)

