### **Analysis Plan:**

P-values of 0.05 or less will be considered statistically significant based on a two-sided test unless otherwise noted. All variables will be tabulated descriptively at each scheduled time point. For each continuous variable, the analyses will include the mean, standard deviation, minimum and maximum. For each categorical variable, the summary will include frequencies and percentages. Each variable will be analyzed using all available data. Baseline variables will be summarized using descriptive statistics. Between-group differences for primary and secondary endpoints will be explored at the time of the last treatment visit (weeks 12) and every two weeks of treatment.

Additionally, the retention of potential benefit will be assessed at the time of follow-up visit following the completion of treatment (two weeks post termination of treatment). The frequency of subjects

with adverse events (AEs) will be tabulated. AEs will also be tabulated by severity and, when appropriate, by relationship to study treatment. The difference in the occurrence of adverse events between the study groups will be compared descriptively.

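### The fall log is tied to a four-week study period that matches neither stated timetable, so read literally it leaves 50% or 71% of follow-up outside the log

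*Combined protocol and SAP*

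**What the plan says.** The fall log appears once, in the row of Table IV headed Other assessment. The participant receives a log and will "agree to call the study overseer in the event of a fall during the 4 weeks study period".

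The document gives two timetables, and neither is four weeks long:

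- Section 1: "The study consists of a 12 weeks treatment phase and two weeks of retention". The Analysis Plan agrees, stating that between-group differences "will be explored at the time of the last treatment visit (weeks 12) and every two weeks of treatment", with a retention visit two weeks after treatment ends.
- Section 4: "four additional visits at 2 weeks, 4 weeks, 6 weeks during treatment and 8 weeks (2 weeks post stopping the treatment". Table IV agrees, listing follow-up at "week 2, week 4, week 6, and week 8".

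On falling as a hypothesis, H6 in Section 1 states: "The risk and fear of falling during activity of daily life will be improved". The text on Hypothesis 6 under Specific Aim 3 names the measures. Fear is measured with the Fall Efficacy Scale. For risk it says "The risk of falling will be assessed using test timed Up&Go", together with the time taken to rise from or sit on a chair. The fall log is not among these measures, and the Analysis Plan names no analysis of fall counts.

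**The concern.** Table IV is what site staff work from, so the stated length of the log is an operative collection rule. A site that follows it literally stops logging falls at week 4, while participants are still on treatment under either timetable, and logs none after treatment stops. A site that takes the phrase to mean the whole study carries on. Section 3 names two recruiting centres, so both practices could occur in one trial and the time at risk covered by the log would differ between centres.

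Two things are at stake. The first is safety capture: apart from fall history at baseline, the log is the only item in Table IV that records falls themselves, and no fall question is listed for the two-weekly visits. The second is planning: Section 1 says that preliminary data from this study will be used to design a later randomized trial with reduction of falls among its outcomes. A log of uncertain length gives that trial a poorer estimate of the fall rate.

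**Working it through.** **Inputs**

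- Fall-log period: 4 weeks (Table IV, Other assessment).
- Timetable A: 12 weeks of treatment + 2 weeks after (Section 1; Analysis Plan).
- Timetable B: 6 weeks of treatment + 2 weeks after (Section 4; Table IV visit rows).
- Participants: 80 (Sections 3 and 14).

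**Step 1. Can the four weeks be matched to any stated period?**

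| | Treatment | Total | Equal to 4 weeks? |
|---|---|---|---|
| Timetable A | 12 | 12 + 2 = 14 | Neither |
| Timetable B | 6 | 6 + 2 = 8 | Neither |

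Week 4 is an interim visit under timetable B. It ends no phase under either timetable.

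**Step 2. Share of follow-up outside the log**

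Share = (total − 4) / total.

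- Timetable B: (8 − 4)/8 = 50%.
- Timetable A: (14 − 4)/14 = 10/14 = 71%.

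These two shares hold wherever the four weeks fall. If the log starts at baseline, which is the natural reading, the share of the treatment phase outside it is (6 − 4)/6 = 33% under B or (12 − 4)/12 = 67% under A, and the two post-treatment weeks are outside it entirely.

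**Step 3. Person-time, ignoring dropout**

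- Logged: 80 × 4/52 = 6.2 person-years.
- Total under B: 80 × 8/52 = 12.3 person-years.
- Total under A: 80 × 14/52 = 21.5 person-years.

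**Step 4. Illustration in falls**

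The document gives no fall rate. Assuming 0.5 to 1.5 falls per patient-year, constant over time:

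- Logged: 6.2 × 0.5 to 6.2 × 1.5, about 3 to 9 falls.
- Total under B: 12.3 × 0.5 to 12.3 × 1.5, about 6 to 18 falls.
- Total under A: 21.5 × 0.5 to 21.5 × 1.5, about 11 to 32 falls.

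The percentages in Step 2 do not depend on this assumed rate.

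**Step 5. Is there another route for later falls?**

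Section 8 lists adverse events as a data source. Section 11 has the principal investigator review adverse-event patterns and participants' experience at least monthly. The Analysis Plan tabulates adverse events with no four-week limit. A later fall could therefore reach the data. However, no section says that a fall counts as an adverse event, or how events are to be asked about at visits.

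**The case against.** The strongest objection is that the phrase is leftover wording. It presents four weeks as the length of the study, not as a cut-off partway through, so the intention may well have been to log falls throughout. On that view the defect is a by-product of the wider conflict between 8 and 14 weeks. This is plausible, and it means that the shares above describe the literal reading and not a deliberate choice. It does not clear the text: the stated period is wrong under both timetables, and settling the overall duration would not by itself change this line.

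The objection also disposes of several stronger readings that a reader might infer:

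- *That falling is the main hazard the trial names.* Section 10 names no fall hazard. It reports no identified device risk, then loss of confidentiality and unknown side effects. Falling enters through the aim stated in Section 1; the eligibility criteria contain no fall-history requirement.
- *That Hypothesis 6 loses its endpoint.* Its named measures do not use the log. Table IV does omit the timed Up&Go and lists a fear-of-falling scale only at baseline, but that is a separate gap and does not make the log the endpoint.
- *That a fall after week 4, or one not phoned in, is lost.* The participant also holds a written log, and adverse-event recording has no four-week limit.
- *That the retention claim is undermined.* The planned retention analysis is a paired comparison with week 12 of the study's outcomes, and fall counts are not a named outcome.

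Finally, on the assumed rates even a complete log would hold few falls (about 6 to 18 across both arms over 8 weeks). It could not reliably show a difference between arms. That limits the benefit of the correction to description and planning.

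**Conclusion.** The point stands as an internal inconsistency that should be fixed. The log's stated period agrees with no period in the document. Read literally, it leaves 50% (8-week timetable) or 71% (14-week timetable) of follow-up outside the only Table IV item that records falls after baseline. That includes all of the post-treatment period if the log starts at baseline.

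The harm is confined to safety capture, consistency between the two centres, and the preliminary fall data for the later trial. No hypothesis loses its measure and no planned analysis is invalidated. Whether later falls would be picked up as adverse events is left open: the document allows it but does not ensure it.

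The contradiction and the two percentages rest on the document's own durations. The literal reading of the phrase is an assumption, and so is the fall rate used to express the gap as numbers of falls.

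**What to change.** In Table IV, replace the four-week limit on the fall log with wording that runs it *from the baseline visit to the last follow-up visit*. This is correct under either timetable, so it need not wait for the overall duration to be settled. Add that the coordinator reviews the log with the participant at each visit already scheduled.

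Separately, reconcile the 8-week schedule (Section 4; Table IV visit rows) with the 14-week schedule (Section 1; Analysis Plan).

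The cost is one line in Table IV, a log printed for the full period, and about a minute at each existing visit. No new visits or staff are needed.

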**Specific Aim 1:** Our first goal is to compare postural control in subjects assigned to use the active Electrical Stimulation (intervention group) and subjects assigned to non-functional stimulator (sham group). Balance will be assessed for both groups at baseline and at bi-weekly intervals. Static balance and postural compensatory strategy will be assessed using the body worn sensor technology (BalanSens™) explained in the preliminary study #1. The duration of assessment is approximately five minutes. The test includes quiet upright standing for a period of at least 30 seconds under two conditions: eyes-open and eyes-closed. Postural control will be quantified by measuring the range of motion of center of mass (COM) in medial-lateral and anterior-posterior direction. COM is estimated using an innovative and validated technology based on wearable sensors as explained in our preliminary study #1 – Figure 12. The key advantage of this technology is that balance is assessed outside of gait laboratory and directly in our podiatric center. Additionally, it allows measuring directly COM instead of center of pressure (COP). Our recent study suggests that measuring COM is 12 times more sensitive to assess postural instability than COP (Figure 3) (Najafi, Horn et al. 2010).

**Figure 12:** Balance will be assessed according Romberg protocol and will be quantified using a validated technology based on body worn sensors

**Figure 13:** An innovative device based on body worn sensors allows measuring spatio-temporal parameters of gait and gait initiation in free condition including outside of a gaitlab.

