
For the purpose of gait analysis, subjects will be asked to walk at their habitual speed in a distance of approximately 20 meters while wearing the gait analyzer sensors (Fig 13). The system allows extracting over 30 spatio-temporal parameters of gait including stride velocity, stride length, stride time, stance, double support time, COM in medial-lateral and anterior-posterior, and gait initiation(Najafi, Helbostad et al. 2009; Najafi, Miller et al. 2010). We assumed that the performance of gait and dynamic balance will be improved in the intervention group after treatment compared to baseline and compared to sham group (Hypothesis 2). Additionally, we anticipate that the inter-cycle gait variability and gait initiation will be improved after treatment in the active group compared to

[figure not shown]
baseline and compared to sham group.

**Specific Aim 2:** Our second aim is to compare changes in skin perfusion in patients treated with Electrical Stimulation (ESTIM) compared to sham therapy. We anticipate that electrical Stimulation will improve dorsal and plantar perfusion compared to the control group and compared to baseline (Hypothesis 3). As described in the clinical assessment (Table IV), we will assess perfusion of the macro-circulation with arterial Doppler studies and micro-circulation with Skin Perfusion Pressure measurements and transcutaneous oxygen measurements.

**Specific Aim 3:** Our last aim us to evaluate changes in quality of life in high risk diabetes that receive Electrical Stimulation compared to sham therapy. Our hypotheses and methods of assessment described in the following:

Hypothesis 4: We assume that plantar electrical stimulation will improve subject quality of life in the intervention group. Quality of life will be assessed using SF-12 questionnaire (Melville, Lari et al. 2003) at the baseline visit and at week 6.

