To determine whether gait, balance, and physical activity variables change significantly across different study visit epochs, within-subject analyses of variance (ANOVA's) will be employed. We assume that plantar electrical stimulation is helpful to improve subjects gait, balance, and physical activity. Then sensor-derived movement variables should change substantially from baseline to the end of the study for the active group with no significant change in placebo group. For example, the range of motion of COM and RCI values should be reduced and gait velocity should be increased. Next, for all continuous variables, pretreatment scores will be regressed on post-treatment scores to form residualized change scores (e.g. VPT, monofilament test, pain intensity, A1C, etc). Correlations will then be generated among these scores to determine whether changes in sensor-derived movement factors are related appropriately with increases in (clinically assessed) functional capacities and self-report measures of activities, mood, socializing, etc. ANOVA test will be used to examine significant difference between intervention and sham group at baseline for age and BMI as well as the indicated outcomes (e.g. gait, balance, VPT, ABI,. Etc). We assumed there is no significant difference between sham and intervention group at baseline for the indicated variables. The same test will be repeated for the week 12. We assumed that the outcomes of study will be improved in the intervention group compared to the sham group. Paired- sample t-test will be used to examine the retention of the electrical stimulation therapy at two weeks post stopping the therapy compared to week-12. We assumed the benefit of the electrical stimulation therapy will be retained at least for two weeks. Additional analyses will examine the degree to which early-treatment changes in cognitive variables and functional capacity variables (representing functional restoration processes) predict late-treatment changes in moving ability post plantar electrical stimulation therapy. Such analyses will also allows to elucidate the relative contributions fear of falling (assessed using FES score); and/or and range of motion (assessed using body worn sensors) made to bringing about clinically meaningful changes in gait balance control. Moderator effects will also be examined for exploratory purposes. Using gender as an example, mixed design ANOVA's will be conducted to determine whether gait and balance factors change over the course of treatment at different rates or with different patterns for men and women as well as for patients with high or low severity of neuropathy and peripheral vascular disease. We assume those who have higher peripheral vascular problem will receive maximum benefit from electrical stimulation. Additional analyses will test whether changes in gait and balance variables predict changes in clinically important outcome factors (e.g., fear of falling (FES) , quality of life (SF12), adverse events, foot ulcer, etc) depending on gender.

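### No primary endpoint, condition or time point is designated, and one unadjusted 5% rule covers an open list of outcomes, so neither the 5% level nor the 85% power belongs to a declared primary test

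*Combined protocol and SAP*

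**What the plan says.** - **Endpoints.** The Analysis Plan (Section 14) states: "Between-group differences for primary and secondary endpoints will be explored at the time of the last treatment visit". Week 12 and two-weekly comparisons follow. No variable is called primary or secondary anywhere. Section 1 lists three aims and six hypotheses (H1 to H6) without ranking them.
- **Decision rule.** "P-values of 0.05 or less will be considered statistically significant based on a two-sided test unless otherwise noted". No hierarchy or adjustment is given.
- **Between-group test.** ANOVA at baseline is applied to age and BMI "as well as the indicated outcomes (e.g. gait, balance, VPT, ABI,. Etc", and then "The same test will be repeated for the week 12". Within-subject ANOVAs across visits, paired t-tests, correlations and moderator analyses are added.
- **Outcome pool.** Under Specific Aim 1: "The system allows extracting over 30 spatio-temporal parameters of gait". Table IV names about eight gait measures as examples, three stances with eyes open and closed, several walking conditions, vascular measures, neuropathy tests and questionnaires.
- **Balance.** Specific Aim 1: "Postural control will be quantified by measuring the range of motion of center of mass (COM) in medial-lateral and anterior-posterior direction". The sample-size paragraph uses COM sway area in cm².
- **Sizing.** Section 14 aims for 85% power at a two-sided 5% level, with 50% against 10% improvement in subjects evaluable for vibration perception threshold (VPT) and monofilament testing, giving 27 per group. It then states 27 per group again from the Study 5 sway data. The enrolled number is 40 per group.

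**The concern.** A two-sided 5% level is a property of one test chosen in advance. When the plan does not say which test that is, any of many nominally significant results can be presented as the trial's finding. Here that could be a gait parameter, a sway measure in one stance, a perfusion reading or a questionnaire score. Section 14 raises the stakes by saying that a statistically detected difference may be taken as clinically meaningful. H1 and H2 also count improvement from baseline, a second route to success that does not need the sham comparison.

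The power statement has the same gap. VPT and monofilament, the first sizing basis, appear in none of H1 to H6, and the plan describes ANOVA but no comparison of improvement rates. COM sway area, the second basis, belongs to H1, but the stance and vision condition behind the pilot values are not given in Section 14 or in the Study 5 summary.

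**Working it through.** **1. The plan's own figure.** Inputs from Section 14: 0.50 and 0.10, two-sided 5% (z = 1.960), 85% power (z = 1.036); mean proportion 0.30.

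n = [1.960·√(2·0.30·0.70) + 1.036·√(0.50·0.50 + 0.10·0.90)]² / 0.40² = 21.96.

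With continuity correction: (21.96/4)·[1 + √(1 + 4/(21.96·0.40))]² = 26.7, so 27 per group. The stated figure is reproduced, as a comparison of two proportions.

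**2. Chance of at least one false positive.** Assumptions: no true effect, k outcomes each tested once between arms at two-sided 0.05. The documents give neither k nor the correlation.

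If independent, either direction: 1 − 0.95^k. Benefit direction only: 1 − 0.975^k. Correlated cases are simulated with equally correlated normal statistics.

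| Tests (k) | Correlation | Either direction | Benefit direction |
|---|---|---|---|
| 6 | 0.7 | 16% | 8% |
| 10 | 0 | 40% | 22% |
| 10 | 0.5 | 28% | 14% |
| 10 | 0.7 | 21% | 11% |
| 30 | 0 | 79% | 53% |
| 30 | 0.3 | 66% | 35% |
| 30 | 0.5 | 50% | 25% |
| 30 | 0.7 | 34% | 17% |
| 30 | 0.9 | 17% | 8% |

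Independent tests needed to pass 50%: 14 in either direction (1 − 0.95^14 = 51%), or 28 in the benefit direction (1 − 0.975^28 = 51%).

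Repeated visits add to this. For 30 outcomes at three visits, with an assumed visit correlation of 0.8, the figures are 76% and 40% at outcome correlation 0.5, and 55% and 28% at 0.7.

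**3. Power if COM sway area is the primary.** Inputs from Section 14, sham then active: baseline 5.23 (SD 2.81) and 5.41 (SD 1.14); week 2 4.94 (SD 3.42) and 3.49 (SD 1.25) cm². Below, (1.960 + 1.036)² = 8.978.

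- *Unadjusted, week 2.* Difference 4.94 − 3.49 = 1.45; sum of variances 3.42² + 1.25² = 13.26. n = 8.978·13.26/1.45² = 56.6, so 57 per group. At 40 per group: SE = √(13.26/40) = 0.576, and 1.45/0.576 = 2.52. Power is about 71% by the normal approximation and 70% by the t distribution.
- *Change from baseline.* Difference in change (5.41 − 3.49) − (5.23 − 4.94) = 1.63. With pre-post correlation r, assumed equal in both arms, the summed variance of change is 22.45 − 22.07r. So n = 8.978·(22.45 − 22.07r)/1.63², about 75.9 − 74.6r. This gives 27 at r of about 0.66 and 40 at r of about 0.48. The plan states no r.

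**4. Which visit.** Section 1 and Section 14 use a 12-week treatment phase. Section 4 and Table IV put the treatment visits at weeks 2, 4 and 6 and the post-treatment visit at week 8. The last treatment visit, and the number of test occasions, cannot be fixed until these passages are reconciled.

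**The case against.** A reader might infer that every one of more than 30 gait variables, with sway, perfusion and questionnaires, is tested at each visit, so that a false benefit is more likely than not. The documents do not support this.

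- The sentence on 30 parameters describes what the device can extract, not a list of tests.
- The formal between-group ANOVA is stated for baseline and week 12; two-weekly differences are only to be explored.
- SF-12 is given at baseline and week 6 only.
- Stride velocity, length and time are arithmetically linked, so independence is unrealistic. With 30 tests at one time point, the chance of a false benefit is already 35% at correlation 0.3.

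It can also be said that the study is meant to supply preliminary data for a later trial, and that the power statement is not empty: it specifies an active-versus-sham contrast, two rates and a level, and its 27 can be reproduced.

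These points limit the size of the problem but do not remove it. The word for exploration sits beside a significance rule, a power target and directional hypotheses. The reproducible calculation rests on an outcome that no hypothesis contains and on a type of test that the analysis text does not describe.

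**Conclusion.** The point holds as a gap in specification with a real effect on error control. No variable, condition or time point is primary, two outcomes compete as the sizing basis, balance has two metrics, and nothing controls multiplicity across six unranked hypotheses.

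The family-wise error exceeds 5% in every multi-outcome scenario that was run. How far it exceeds 5% depends on the number of tests and their correlation, both assumed here. The 30-test figures show what the plan permits; they do not predict this trial's error rate. A claim that a false benefit is more likely than not is not established.

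The power figure of about 70% assumes that the printed week-2 pilot means and SDs carry over to the primary time point and that all 40 per group are evaluable.

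**What to change.** In Section 14, before unblinding:

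1. **Name one primary endpoint.** COM sway area is the natural choice, because it serves Aim 1 and H1 and is one of the two sizing outcomes. If VPT or monofilament response is intended instead, say so and plan the matching test. The choice is the sponsor's.
2. **Define it fully.** Use one metric (area or range of motion) and one stance and vision condition. Compare the arms, preferably adjusted for baseline, at the last treatment visit once the week 6 and week 12 passages are reconciled, at two-sided 5%.
3. **Rank the rest.** Name one lead variable for each other hypothesis as secondary, under a stated rule such as Holm. Report all other variables, visits and within-group changes as estimates with 95% confidence intervals and no significance claim.
4. **Restate the power** for the chosen primary, giving any pre-post correlation relied on and its source.

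The cost is plan wording and a short recalculation, with no new data collection. Fewer variables can be called significant, and the restated power may be less favorable than 85%.
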